**Document Date: December 15, 2016**

**NCT01504438**

## Prospective Randomized Evaluation Of A Two And Three Piece Total Ankle Replacement

**Purpose of the Study** – Randomized study to prospectively compare and evaluate the functional outcome and patient satisfaction of total ankle replacements for tibio-talar osteoarthritis using either the STAR or Salto-Talaris prothesis.

**Background & Significance** – The primary articulation of the ankle joint is between the tibia and talus. This joint is subjected to extreme forces during daily activity and therefore is susceptible to the development of osteoarthritis. Severe osteoarthritis of the ankle is treated either by joint fusion or replacement. Traditionally, most orthopaedic surgeons have opted for joint fusion over replacement because of the high failure rates and poor technology of total ankle replacements. However, newer total ankle replacements are being introduced with better results, largely due to borrowed technology from the tried and true fields of total hip and knee replacement. Therefore, more surgeons are opting for ankle replacement to preserve ankle motion and prevent adjacent joint osteoarthritis often seen with ankle joint fusion. In the US at present time, there is a single 3 piece ankle prothesis (STAR) and several 2 piece (Salto-Talaris, InBone, Agility) approved for use. Currently there is debate in the orthopaedic community about whether a 2 piece or 3 piece ankle replacement is superior in terms of longevity, satisfaction, and function. This study will evaluate patient satisfaction and functional outcome of total ankle replacement for ankle osteoarthritis by one of two different currently available and approved ankle prothesis, the STAR and the Salto-Talaris.

**Design & Procedures** – Adult patients (age > 18 years) who have severe osteoarthritis of the ankle joint significant enough to be treated with a total ankle replacement as determined by Drs. [name], [name], or [name] with the aid of the physical exam and routine radiography, treated at Duke University Medical Center will be asked to participate in this study. After routine surgical counseling by Drs. [name], [name], [name] or [name], those patients meeting the inclusion criteria will be asked to participate in this study by their attending physician. The consent form will be administered in the clinic. No PHI will be collected prior to consent. If a patient chooses to participate, they will be asked to sign the consent form and will be asked to complete the following patient outcome questionnaires (attached): Visual Analog Pain Scale, Short-form 36, AOFAS hind foot score, a Short Musculoskeletal Function Assessment questionnaire and FADI. Also at this time patients will be randomly assigned to receive either the STAR or Salto-Talaris ankle prosthesis at the time of their surgery. There will be 80 individual, sealed, opaque sequentially numbered envelopes containing the randomization of either ankle prosthesis (40 of each implant). The patient will then undergo surgery as scheduled at a later date. Participants will be in the study a total of ten years.

Following surgery, the patient will present for routine follow-up appointments. At the six month, one year, two year, three year visit and every year thereafter, the patients participating in the study will be asked to complete the previously mentioned outcome questionnaires. These are all normal follow-up visit time points; the patients will not be asked to return to clinic for any additional visits that would not be routine. At each visit, the patient will also receive plain x-rays. Plain x-rays are part of routine follow-up and not additional tests for this study.

The study will proceed until a minimum of ten-year follow-up is achieved for all patients. We will leave the ten year window open for all subjects until the last subject has finished their ten year time point. This will ensure that all subjects will have an appropriate time span in order to return for their standard of care visit.

All patients who receive a total ankle replacement at Duke is asked to complete a set of questionnaires (Visual Analog Scale, Short Musculoskeletal Function Assessment, Short Form-36 Health Survey, Foot and Ankle Outcome Score Questionnaire, AOFAS Ankle-Hindfoot Scale) as part of the Duke Orthopaedics Foot and Ankle physicians' standard of care. We will ask subjects permission to use these questionnaires that have been collected from them since their randomized TAR surgery. We are also asking subjects permission to release their de-identified study information to orthopaedic equipment manufacturers, and to continue their follow-up to their 10-year post-operative time point. A letter will be mailed to all subjects explaining the change. This letter is explained in the Consent Process section. Drs. [name], [name], [name], [name] will only be recruiting their own patients

**Subject identification, recruitment, and compensation**- Inclusion/ Exclusion criteria: Adult patients (age > 18 years) who will benefit from a total ankle replacement, as determined by Drs. [name], [name], [name] or [name], with the aid of the physical exam and routine radiography treated at Duke University Medical Center and who have no medical conditions that would represent contraindications to surgery or anesthesia will be

asked to participate in this study. The only excluded patients will be those who do not choose to participate in this study, have a weight greater than 230lbs, or do not meet the minimum age of 18 years. Drs. [name], [name], or [name] will only be recruiting their own patients. Drs. [name], [name], [name] or [name] will not personally obtain consent due to a conflict of interest related to their consulting relationship with Tornier Inc and SBI Inc. Approximately 100 DUHS patients will be recruited to undergo either a STAR or Salto-Talaris Total Ankle Replacement. Study enrollment will be complete once 50 of each cohort have been treated. There is no compensation associated with participation in this study.

**Consent Process** – Upon determination that a subject is compatible with the eligibility criteria of the protocol, the study will be explained to the subject by the investigator or his/her authorized designee. If the subject indicates interest in participating in the study, the informed consent document will be provided to the patient since these documents provide a comprehension explanation of the study in lay terms. If the subject continues to show interest, the investigator or his/her authorized designee will thoroughly explain to the subject the required elements of informed consent and all aspects of the study (i.e., inclusion/exclusion criteria, risks, benefits and alternatives to the study, etc.).

The subject will receive a copy of the study consent form and the signed and dated original copy will be retained in the subject's study file or medical record.

[name] has a consulting relationship with SBI and therefore is not able to sign the informed consent and will have approved IRB personnel to do so.

A letter will be mailed to all patients previously consented to this study, explaining the changes made to the study protocol. Along with this letter two consent forms, one for subjects to keep and the other to send back, will be included in this packet. If subjects return to clinic and have not yet signed and returned the consent form that was mailed we will approach them in clinic and explain the additions to the study. Patients will be given a copy of the study consent form, and the signed and dated original copy will be retained in the subject's study file or medical record.

**Subject's Capacity to Give Legally Effective Consent** – Only those subjects able to read and comprehend the consent form will be asked to participate in this study.

**Risk/Benefit Assessment** – There is a minimal risk of loss of confidentiality. If a patient chooses not to participate, they will receive the total ankle replacement as planned.

**Costs to the Subject** – There will be no cost to the subject associated with this study.

**Data Analysis & Statistical Considerations** – The data will be summarized using routine descriptive statistics. The following clinical outcome parameters will be analyzed using a series of 2X4 between subject repeated measures ANOVAs, with Tukey post hoc testing to determine statistically significant differences. The 2 X 4 ANOVA will be comparing the 2 groups (Salto Talaris and STAR implants) and the five time points of interest (pre-op, 6 months, 1 year, 2 years, and 3 years following surgery). The clinical outcome variables of interest will be the visual analog pain scale, foot and ankle disability index, the SF-36, the AOFAS hind foot score, and the short form musculoskeletal assessment. In addition, radiographic measurements will be collected on the radiographs that are available in the patients' medical record at each of the pre and post-operative time points. Monitoring of data will not be done until the final analysis after all data is collected. A p-value less than 0.05 will be used as the level of statistical significance for this study.

**Data & Safety Monitoring** - Monitoring data for safety is a function of the PI and study team. The PI will be responsible for review and sign off on all adverse events and/or problems as they occur and report adverse events and/or problems as required by HRPP policies to the IRB.

**Data storage & confidentiality** – The principal investigator and co-investigators will collect data in a computerized database using a commercially available database program. During collection, data will be indexed by the patient's medical record number. After data collection, a case number will be assigned to the data, and the medical record number (the only identifying data collected) will be stripped from the database. The code linking medical record number to case number will be kept in a locked file with access limited to the primary investigator. When the study is complete the code linking medical record numbers to case numbers will be destroyed. During data collection and review protected health information will be available only to the principal investigator and co-investigators and will not be reused or disclosed to any other person or entity, except as required by law, for authorized oversight of the research study.

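### The implant is assigned at the consent visit, before a later surgery, and enrolment is counted on treated patients, so withdrawals or switches after assignment can go unseen

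*Combined protocol and SAP*

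**What the plan says.** Under Design & Procedures, a patient who agrees to take part does two things in clinic: "they will be asked to sign the consent form and will be asked to complete the following patient outcome questionnaires (attached". Allocation comes in the next sentence: "Also at this time patients will be randomly assigned to receive either the STAR or Salto-Talaris ankle prosthesis at the time of their surgery". The operation is a separate, later event: "The patient will then undergo surgery as scheduled at a later date". The interval is not given. Concealment is by envelope: "There will be 80 individual, sealed, opaque sequentially numbered envelopes containing the randomization of either ankle prosthesis (40 of each implant".

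Under Subject identification, recruitment, and compensation, the target is stated as "Approximately 100 DUHS patients will be recruited to undergo either a STAR or Salto-Talaris Total Ankle Replacement", and the closing rule is "Study enrollment will be complete once 50 of each cohort have been treated".

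Under Data Analysis & Statistical Considerations, the repeated-measures ANOVA covers "the five time points of interest (pre-op, 6 months, 1 year, 2 years, and 3 years following surgery", and the outcomes are "the visual analog pain scale, foot and ankle disability index, the SF-36, the AOFAS hind foot score, and the short form musculoskeletal assessment".

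Three things are not stated anywhere:
- who learns the allocation, and when;
- which patients form the analysis set;
- what happens to a patient who withdraws or changes implant between assignment and surgery.

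**The concern.** Sealed, opaque, numbered envelopes protect the allocation until they are opened. After that, protection depends either on masking, which the plan does not describe, or on leaving little time between assignment and treatment. The plan opens the envelope at consent, so there is an interval in which the device may be known and the operation has not taken place. The patient may reconsider. The surgeon may too: the plan declares that the surgeons have consulting relationships with two companies and recruit their own patients, and it deals with that conflict only for the taking of consent.

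The closing rule makes the gap matter more. Because it counts treated patients, someone randomised and then lost before surgery does not use up a place. If such losses differ by arm and relate to prognosis or expectation, the treated groups are no longer the randomised groups, and nothing in the planned reporting would show it.

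A second, lesser issue concerns baseline. The pre-operative score is one of the ANOVA time points and the outcomes are largely patient-reported. If a patient learned the implant before completing the forms, any resulting difference between arms at baseline would enter the group-by-time interaction.

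**Working it through.** The plan has no sample-size calculation, standard deviation, correlation or dropout rate, so there is no figure of its own to reproduce. The loss rates, shifts and correlation below are assumptions.

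**1. Sequence and counting.** Read together, the sections give this order: consent and questionnaires, assignment at the same visit, surgery later, and a patient counted only once treated. Nothing records or reports a patient who drops out between assignment and surgery.

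**2. Patients outside the count.** To reach m treated per arm with a pre-surgery loss d, the number to randomise is m / (1 - d), rounded up. With m = 50 from the closing rule:

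| Assumed loss | Per arm | Total randomised | Randomised, not treated |
|---|---|---|---|
| 5% | 50/0.95 = 52.6, so 53 | 106 | 6 |
| 10% | 50/0.90 = 55.6, so 56 | 112 | 12 |
| 20% | 50/0.80 = 62.5, so 63 | 126 | 26 |

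A tally of 50 and 50 treated fits every row. (The 80 envelopes, 40 per implant, cannot supply 100 treated patients at any loss rate. That is a separate inconsistency and the reason both 50 and 40 per arm appear below.)

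**3. Baseline shift, only if the envelope came first.** Assume no true implant effect, unit SD, correlation r = 0.5 between all pairs of time points, and an artificial between-arm difference s at the pre-operative point only. The text calls the ANOVA 2X4 but lists five time points; I use k = 5.

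For the group-by-time F test, df1 = k - 1 = 4 and df2 = 4(2n - 2). The noncentrality is (n/2) × s² × (1 - 1/k) / (1 - r), which with k = 5 and r = 0.5 is 0.8 × n × s².

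| n per arm | s | Noncentrality | df2 | Chance of p < 0.05 |
|---|---|---|---|---|
| 50 | 0.1 | 0.8 × 50 × 0.01 = 0.40 | 392 | 7.0% |
| 50 | 0.2 | 0.8 × 50 × 0.04 = 1.60 | 392 | 14.3% |
| 40 | 0.1 | 0.8 × 40 × 0.01 = 0.32 | 312 | 6.6% |
| 40 | 0.2 | 0.8 × 40 × 0.04 = 1.28 | 312 | 12.2% |

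The group main effect hardly moves. Its noncentrality is (n/2)(s/5)²/0.6, where 0.6 = (1 + 4 × 0.5)/5 is the variance of a patient's mean. At n = 50 and s = 0.2 this is 25 × 0.0016/0.6 = 0.067, giving 5.8%.

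If both arms shift equally, s = 0, the noncentrality is zero and the error stays at 5%.

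**The case against.** The strongest objection is to the baseline part, and most of it stands. The plan names the questionnaires before the assignment. Followed in that order, the allocation cannot affect the answers and the harm is zero. A reader might infer from the shared visit that baseline is measured after allocation, but the text says only that both happen on one occasion. What is missing is a rule and a record of the order. The plan also offers no reason why knowing which of two approved implants is coming would move scores differently by arm; its background says their relative merit is under debate.

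Three other readings go beyond the documents.
- A reader might say allocation occurs well before surgery. Only a later date is given, and since surgery goes ahead as scheduled, the date may already be fixed at assignment.
- A reader might call the trial open label. That is a reasonable inference from the silence on masking, but it is not stated.
- A reader might size the baseline effect with a two-sample t test on change scores, which gives about 8-17% at 50 per arm. That is not the planned test.

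It may also be said that patients who leave or switch need not be lost to outcome. This is partly right. Everyone who receives an ankle replacement at the centre is asked for standard-of-care questionnaires, and these include four of the five trial outcomes (not the foot and ankle disability index). Data may therefore exist, subject to permission. But no rule says they would be analysed under the assigned arm.

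Finally, this version mentions patients already consented and already operated on, and does not say whether enrolment is still open. For those patients the envelope timing cannot be changed. The reporting can.

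**Conclusion.** The point holds for the interval between assignment and surgery. Assignment at consent, a later operation, no described masking and a closing rule based on treated patients together allow losses or switches after assignment to be replaced and left out of the count. The possible size is 6 to 26 uncounted patients for 100 treated, if 5% to 20% are lost. Those rates are assumed, and nothing in the documents shows that such losses occurred or differed by arm. The point also rests on the inference that patient or surgeon learns the device when the envelope is opened.

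The order of questionnaires and envelope is a secondary safeguard. If the order were reversed, and only then, an assumed differential shift of 0.1-0.2 SD at correlation 0.5 would raise the error of the group-by-time test from 5% to about 7-14% at 50 per arm, or 7-12% at 40. The documents do not support saying that baseline scores are contaminated.

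**What to change.** For any enrolment that remains, state in Design & Procedures that the next envelope is opened at the latest point before surgery that implant ordering allows, not at the consent visit, and only once the baseline questionnaires have been completed and collected. Record both dates for each patient.

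For all patients, including those already enrolled, add to Data Analysis & Statistical Considerations that everyone randomised is reported by assigned arm, including those not treated and those who received the other implant. Retrieve the two dates for past patients where they were recorded. The plan defers review of the data to the final analysis, so this can still be laid down beforehand.

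Fixing the order of forms and envelope costs nothing. Opening the envelope later means the device set is known later. The documents say nothing about ordering, so that cost is assumed to be small; tying the rule to ordering limits it. Full reporting requires only a log of envelopes opened.

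### The protocol provides 80 randomisation envelopes (40 per implant) but closes enrolment only at 50 treated per implant, and describes no allocation method after envelope 80

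*Combined protocol and SAP*

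**What the plan says.** Under Design & Procedures, the supply of assignments is fixed: "There will be 80 individual, sealed, opaque sequentially numbered envelopes containing the randomization of either ankle prosthesis (40 of each implant"). Assignment takes place at the consent visit: "Also at this time patients will be randomly assigned to receive either the STAR or Salto-Talaris ankle prosthesis at the time of their surgery". Surgery comes afterwards: "The patient will then undergo surgery as scheduled at a later date".

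Under Subject identification, recruitment, and compensation, the size is different: "Approximately 100 DUHS patients will be recruited to undergo either a STAR or Salto-Talaris Total Ankle Replacement". The closing rule follows: "Study enrollment will be complete once 50 of each cohort have been treated".

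The protocol mentions no further envelopes, second list or other way of assigning an implant. Data Analysis & Statistical Considerations gives no sample size, power or dropout allowance, so it does not show which total is intended.

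This version was written with the trial already under way. Design & Procedures says "We will ask subjects permission to use these questionnaires that have been collected from them since their randomized TAR surgery", and Consent Process says "A letter will be mailed to all patients previously consented to this study, explaining the changes made to the study protocol".

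**The concern.** The two sections disagree on the size of the trial and, as a result, on how patients are allocated. If recruitment follows its own closing rule, the only concealed mechanism runs out before enrolment can end.

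Concealment matters in this setting. Attending physicians invite patients, surgeons recruit their own patients, and the protocol declares a conflict of interest arising from the surgeons' consulting work. The safeguard it describes is that the surgeons do not personally obtain consent. It does not cover implant assignment, for which the sealed envelopes are the only protection described.

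Some patients had already been randomised and operated on when this version was written. A reader cannot tell how many were randomised in total, or whether every assignment came from a sealed envelope.

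**Working it through.** **Inputs.** From Design & Procedures: 80 envelopes, 40 per implant, with assignment at consent before surgery. From the recruitment section: about 100 recruited, closing at 50 treated per implant. The documents give no rate of loss between randomisation and surgery.

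**Each figure on its own.** 2 × 40 = 80, so the envelope count is internally consistent. 2 × 50 = 100, so the recruitment figures are too.

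**The two together.** 100 − 80 = 20 assignments, or 10 per implant. That is 20/100 = 20% of the target.

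**Could a dropout allowance explain it?** 80/(1 − 0.20) = 100 matches numerically, but it runs the wrong way. Envelopes must cover everyone randomised, while the 50 per implant are counted after treatment. The number randomised can exceed the number treated but cannot be 20 below it.

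**Why 20 is a minimum.** A patient who is randomised but never operated on uses an envelope without counting towards the 50. Let L be the proportion lost in this way (assumed). Then:

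- treated patients from 80 envelopes = 80 × (1 − L)
- envelopes needed on average = 2 × 50/(1 − L), rounded up within each implant
- chance that exactly 100 envelopes give 100 treated patients = (1 − L)^100, with losses independent

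| Assumed L | Treated from 80 | Envelopes needed | Shortfall against 80 | Chance that 100 suffice |
|---|---|---|---|---|
| 0% | 80 | 100 | 20 | 100% |
| 1% | 79.2 | 2 × 51 = 102 | 22 | 37% |
| 5% | 76 | 2 × 53 = 106 | 26 | 0.6% |
| 10% | 72 | 2 × 56 = 112 | 32 | below 0.01% |

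The last column shows that adding exactly 20 envelopes while still counting treated patients would probably not be enough.

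**Precision, as illustration only.** With equal variances, confidence interval width is proportional to 1/√n per arm. The ratio for 40 against 50 per arm is √(50/40) = 1.118, about 12% wider.

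**The case against.** The strongest reply is that this may be a documentary slip. If enrolment stopped at or below 80, the recruitment section is merely out of date and no allocation was affected. If extra envelopes were prepared but not recorded, the omission is in the text alone. The documents exclude neither possibility, and calling the envelopes short presumes that 100 is the true size, which no sample-size rationale supports. That stands, and it is why the fix depends on what happened. It does not remove the need to correct the text.

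It can also be said that the loss rates are assumed, that the protocol does not say whether an unused assignment is replaced, and that the 12% is not a consequence of the error because no precision target is stated. These points are fair. The finding does not rest on those figures: the contradiction is fully present at zero loss.

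The word approximately softens the 100 recruited but not the closing rule, which is a firm 50 treated per implant.

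Finally, counting treated patients could be kept by preparing more than 100 envelopes. That is workable, so changing the closing basis is a recommendation and not the only possible repair.

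**Conclusion.** The concern holds, and the protocol is wrong as written. It describes 80 concealed assignments and an enrolment rule that needs at least 100. The gap is at least 20 patients (10 per implant, 20% of the target), and no allocation method is given for them. This count needs no assumption. The larger shortfalls of 22, 26 and 32 depend on assumed pre-surgery losses of 1%, 5% and 10%.

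What the documents do not establish is which total is intended, whether recruitment was still open, or whether an 81st patient was ever enrolled. They give no evidence of unconcealed allocation. The contradiction must be fixed because it concerns trial size and allocation in a randomised comparison. The record can still be corrected: follow-up runs to ten years, and the protocol defers looking at the data until the final analysis.

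**What to change.** State one number in both sections, according to the facts:

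1. **If the target is 100:** add envelopes 81–100, 10 per implant, with the order generated and concealed by someone who does not recruit. Close enrolment when 100 patients have been randomised, and analyse each patient in the arm drawn. If the sponsor prefers to keep counting treated patients, prepare a reserve beyond 100 and say what happens when one arm reaches 50 first.
2. **If enrolment ended with the envelopes:** restate the size as 80 (40 per arm) and delete the 50-treated rule.
3. **If more than 80 have already been enrolled:** report the number randomised and how those after the 80th were assigned. Add a sensitivity analysis that excludes anyone assigned without a concealed envelope.

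**Cost.** Options 1 and 2 are wording changes in two sections, plus 20 more envelopes under option 1 if recruitment is still open. Option 3 also requires retrieving the allocation records and, if any assignment was unconcealed, one further analysis. Closing on randomised patients may leave the treated arms slightly below 50 and slightly unequal. Restating the size as 80 gives up the larger target. With any fixed total, someone holding the tally can deduce the last assignment.

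### Usability of routine post-operative forms already on file depends on a later re-consent that is mailed once and then pursued only at clinic return; the analysis plan does not deal with the resulting selection

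*Combined protocol and SAP*

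**What the plan says.** - **Study questionnaires (Design & Procedures).** Patients complete the outcome questionnaires when they consent, then at 6 months, 1, 2 and 3 years, and yearly after that. Nothing in this section ties these forms to a further permission. No visits are added beyond routine care.
- **Routine-care questionnaires (Design & Procedures, standard-of-care paragraph).** These are a second source, already on file: "We will ask subjects permission to use these questionnaires that have been collected from them since their randomized TAR surgery". The same request covers release of de-identified data to manufacturers and permission "to continue their follow-up to their 10-year post-operative time point".
- **How permission is sought (Consent Process).** The first contact is by post and goes to everyone enrolled: "A letter will be mailed to all patients previously consented to this study, explaining the changes made to the study protocol". Patients can reply without a clinic visit, because a form for return is enclosed. After that: "If subjects return to clinic and have not yet signed and returned the consent form that was mailed we will approach them in clinic". No repeat mailing or phone call is described, and nothing is said about patients who have died or cannot be reached.
- **Analysis (Data Analysis & Statistical Considerations).** Repeated measures ANOVAs compare the implants over "five time points of interest (pre-op, 6 months, 1 year, 2 years, and 3 years following surgery". There is no missing-data rule, no analysis set, and no statement on whether routine forms may supply a visit's score.

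**The concern.** In ordinary dropout the visit is missed and no score exists. Here the visit took place and a form is on file, but whether it can be used may be settled years later by whether the patient posts back a form or comes to clinic again. Patients who are dissatisfied, re-treated elsewhere or dead may be less likely to do either. Pre-operative scores were collected under the original consent and escape this filter.

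If routine forms fill gaps in the study series, a repeated measures ANOVA, which by default drops incomplete series, would keep gap-filled patients who re-consented and lose similar patients who did not. If re-consent depends on outcome, improvement from baseline could be distorted. The implant comparison could be distorted too if the selection, or the mix of good and poor outcomes, differs between arms. A rule for missed visits would not reveal this, because the form exists.

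**Working it through.** The documents state no power, SD, dropout, mail-return or clinic-return figure, so there is no plan figure to reproduce. The structure comes from the text; every rate below is an assumption.

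**1. Which outcomes are exposed.** Analysed outcomes: pain scale, FADI, SF-36, AOFAS, short musculoskeletal assessment. Routine set: pain scale, short musculoskeletal assessment, SF-36, Foot and Ankle Outcome Score, AOFAS. Four of the five analysed outcomes overlap; the FADI does not.

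**2. Which patients are exposed under the planned ANOVA.** With complete series required, re-consent changes inclusion only for a patient who lacks at least one study form but has a routine form for every such gap. A patient with no 2- or 3-year score from either source is dropped whether or not they re-consent.

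**3. Coverage of routine forms.** Let m be the mail-back rate, r the clinic-return rate among mail non-responders, and c = 0.9 the agreement rate when approached. Coverage = m + (1 − m) × r × c.
- m = 0.3, r = 0.5: 0.3 + 0.7 × 0.45 = 0.615
- m = 0.8, r = 0.9: 0.8 + 0.2 × 0.81 = 0.962

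That is about 62 to 96 of 100 patients, or 49 to 77 of 80 (the protocol gives both totals).

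**4. Shift in one arm's mean.** Take two equal outcome strata at +0.8 and −0.8 SD, with coverage g and b. Shift = 0.8 × (g − b)/(g + b). With r = 0.9 for the better stratum and 0.5 for the worse:

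| m | g | b | Shift (SD) |
|---|---|---|---|
| 0.3 | 0.867 | 0.615 | 0.136 |
| 0.5 | 0.905 | 0.725 | 0.088 |
| 0.8 | 0.962 | 0.890 | 0.031 |

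With equal return rates the shift is 0. If both arms have the same outcome mix and the same selection, it cancels between implants but stays in change from baseline.

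**5. Implant difference when the outcome mix differs.** Assume 10% and 25% poor outcomes on the two implants, a 1.5 SD gap between poor and good, 90% re-consent after a good outcome, a proportion q of study forms missing independently at each of four post-operative visits, and a routine form on file for every missing one. True difference = (0.25 − 0.10) × 1.5 = 0.225 SD. P(complete) = (1 − q)^4 + [1 − (1 − q)^4] × re-consent rate.

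Example with q = 0.1 and 70% re-consent after a poor outcome: (0.9)^4 = 0.6561. Good: 0.6561 + 0.3439 × 0.9 = 0.9656. Poor: 0.6561 + 0.3439 × 0.7 = 0.8968. Poor share among complete cases: 0.1 × 0.8968/(0.1 × 0.8968 + 0.9 × 0.9656) = 0.0935 in one arm and, likewise, 0.2364 in the other. Observed difference = (0.2364 − 0.0935) × 1.5 = 0.214 SD.

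| q | Complete only through re-consent | Observed difference (SD) if poor-outcome re-consent is 70% / 50% / 30% |
|---|---|---|
| 0.1 | 34% | 0.214 / 0.203 / 0.191 |
| 0.2 | 59% | 0.206 / 0.184 / 0.161 |
| 0.3 | 76% | 0.199 / 0.170 / 0.137 |

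The loss is 0.011 to 0.088 SD, or 5% to 39% of the true difference. It is zero if re-consent is unrelated to outcome or if no study form is missing.

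**6. Scale.** The standard error of a between-arm difference is √(2/n): 0.22 SD with 40 per arm and 0.20 SD with 50. The difference detectable with 80% power at two-sided 0.05 is (1.96 + 0.84) × √(2/n): 0.63 and 0.56 SD.

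**The case against.** The strongest reply is that the packet goes to everyone with a form to send back. A reader might infer that anyone who left the clinic or was re-treated elsewhere cannot contribute. The documents do not support that: a living patient can re-consent by post. Selection is on mail response or return, not on return alone. For patients who died before replying the protocol is silent; excluding their forms, or those of any non-signer, is a natural reading of asking permission but is not stated.

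It can also be said that study questionnaires are scheduled at every analysed visit without any link to the new permission, and that the analysis section never says routine forms fill gaps. This stands. It would be wrong to say that all post-operative data hang on re-consent; the point bites only where routine forms are used.

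The contrast between unfiltered baseline and filtered follow-up is weaker than it looks under a complete-series ANOVA, since a dropped patient loses the baseline score too. That also stands.

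Finally, the calculation in step 5 uses favourable inputs. Study forms are due at routine visits, so a missed visit would normally lose both forms. Having a routine form for every gap implies attendance at all four visits, and such attenders are the patients most easily approached in clinic. Even then the bias is below one standard error. This is fair: the calculation shows a possible mechanism, not an expected size. What remains is that a single mailing followed only by clinic approach is an avoidable source of selection, and that the analysis plan has no rule for it.

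**Conclusion.** The concern holds in a limited form. For four of the five analysed instruments, use of routine post-operative forms already on file depends on a later permission, pursued after one mailing only among those who return. Where those forms supply scores, coverage is selected on later behaviour that may relate to outcome. Neither size nor direction can be derived from the documents; the 0 to 0.136 SD arm shift and the 5% to 39% attenuation rest wholly on assumed rates, and both vanish if re-consent is unrelated to outcome.

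Two stronger conclusions should be avoided. One is that the implant difference will be understated: that requires re-consent to depend on outcome, a different outcome mix between arms, and routine forms actually filling gaps, none of which the documents establish. The other comes from setting the permission to continue to year 10 beside "The study will proceed until a minimum of ten-year follow-up is achieved for all patients": a reader might infer that late follow-up will consist of re-consenters only. The originally consented duration is not visible in the document reviewed, and the stated comparison ends at 3 years, so this cannot be settled here.

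**What to change.** **Consent Process.** Add a second mailing and a phone call to every mail non-responder, whether or not they return to clinic. Ask the IRB whether forms already collected from non-responders and from deceased subjects may be used, and record the answer in the protocol.

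**Data Analysis & Statistical Considerations.** Replace the repeated measures ANOVA with a likelihood-based repeated-measures model that keeps all randomised patients with incomplete series and uses every permitted form. State which source supplies each visit's score. Add a sensitivity analysis restricted to study questionnaires collected under the original consent, and report re-consent by implant. The model does not remove selection that depends on unobserved scores, which is why the sensitivity analysis and the re-consent table are needed.

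Making study forms alone the main analysis is not recommended: it would discard permitted data for a benefit that the documents cannot quantify.

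**Cost.** A few sentences in two sections, one extra mailing and call per non-responder, one IRB question and a little more analysis. No new patients, visits or procedures.
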